An alternative option for the treatment of SOB is oral appliance therapy (OAT). The AASM and the American Academy of Dental Sleep Medicine (AADSM) have provided management guidelines for the utilization of oral appliance therapy (14, 15). Although not as efficacious as CPAP, OAT is indicated for use in patients with mild to moderate OSA who prefer OAT to CPAP, or who do not respond to CPAP, are not candidates for CPAP, or who fail CPAP or behavioral measures such as weight loss or sleep position change. (15) OAT has also demonstrated cardiovascular benefits by lowering blood pressure and reducing mortality (16, 19). OAT has also been shown to have a good adherence rates as determined by mean hours of usage. One example of this is a study by Lowe and others showed an 'index of agreement' of 0.99 between the monitor clock time and the subject's log sheets. In the study, the mean hours of wear was 6.8 hours. (17)

While the benefits and good adherence of OAT are recognized, the efficacy of OAT remains less than optimal (partial response). Using a definition of decreasing Apnea-Hypopnea Index (AHI) to less than or equal to 10, it has been shown that the percent success rates for OAT was: Mild OSA-81%, Moderate OSA-60% and Severe OSA-25%. The mean success rate of OAT was 52% (18).

It would seem prudent that the simultaneous use of both CPAP and OAT (combination therapy) may be beneficial to consider. One pilot study has shown that combination therapy can reduce CPAP pressure (as compared to original PAP titration study) and improve effectiveness of OAT (20). Another study was able to show that OAT could be a short-term alternative to CPAP (21). The study demonstrated that an oral appliance could be as successful, or near successful as CPAP, and as being a convenient option for travel purposes.

There are two primary ways to use combination therapy. One way uses the oral appliance as an anchor for a customizable nasal mask interface (CNMI) while another way uses the patient's preferred CPAP mask separate from the oral appliance. This study will prospectively and randomly assign patients to one of the two combination therapy options and they will use each one for two months. Clinical data obtained during the study will be at one month and at the end of two months and will include: AHI, CPAP pressure, and mask leakage, Nadir, T90, hours of usage and ESS.

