## Methods and Procedures

At least fifty patients who were intolerant to CPAP and had a partial response to OAT (AHI greater than or equal to 5 will be recruited randomly and prospectively into one of two groups (at least 25 each in each group). The group options were: 1} Combination therapy with CNMI and 2) Combination therapy with patient's preferred CPAP mask.

These CPAP intolerant patients underwent a PAP titration during an overnight PSG or were assigned an autoPAP and had accumulated at least one month of data. Intolerance to CPAP was defined as patients who reported to their sleep physician that they were intolerant due to CPAP pressure, mask fit/leak issues. They were also asked to fill out a CPAP intolerance questionnaire to document the reason for the intolerance.

Patients who were determined to be partial responders to OAT were determined to have met an adherence and titration protocol. Adherence was defined as using the oral appliance for at least 4 hours per night for 70% of the nights in the 30-day period leading up to the study. The titration protocol includes a minimum of one month of titration along with using patient testimony, bed partner testimony and overnight oximetry to aid in the titration and when tested with an HST or in-lab PSG, the AHI was greater than or equal to 5 (verification sleep test).

Patients who were assigned the option of using their previously preferred CPAP mask, they underwent one CPAP care session and then the two month time period would begin.

If patients were assigned the CNMI option, they were allowed one week for follow up/adjustments of the customized mask, they also underwent one CPAP care session and then the two month time period would begin.

► Data Analysis and Data Monitoring - Data will be analyzed quantitatively using, but not limited to, the Kolmogorov-Smirnov test, Student's *t* test or the Wilcoxon rank- sum test, and SPSS 12.0 for Windows {Chicago, IL, USA}).

Demographic: Ask patients for age and gender

Physiologic: Weight Scale - Weight+ Ruler - Height= Body mass index (BMI)

Pulse Oximeter: Nadir (low O2 saturation), Time percent below 90 {T90}

Polysomnography {PSG}: Apnea-Hypopnea Index (AHI), CPAP pressure, leakage

CPAP Airview or Data Card: AHI, CPAP pressure, leakage

Home Sleep Study (HST): AHI, Nadir, and T90

► Data Monitoring - At time of start of study at [name] Dental Sleep Medicine, PLLC or at J. [name], P.A. Obtain from patient:

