- 1) CPAP intolerance questionnaire
- 2) Compliance questionnaire with oral appliance
- 3) Obtain CPAP data from PAP titration or autoPAP: CPAP pressure, Leakage, Apnea-Hypopnea Index (AHi), Nadir, Time percent below 90 (T90), hours of usage
- 4) Home Sleep Test (HST): AHi, Nadir, T90
- 5) AutoPAP: AHi, mask leakage
- 6) Gather patient demographics: age, gender, BMI

At one (1) Month

- 1) CPAP intolerance questionnaire
- 2) Compliance questionnaire with Oral Appliance
- 3) Gather CPAP data from "Airview" or Data card: CPAP pressure, leakage, AHi,
- 4) Gather oxygen saturation data from Pulse Oximeter: Nadir and T90
- 5) Optional verification (PSG or HST)

After 2nd Month

- 1) CPAP intolerance questionnaire
- 2) Compliance questionnaire with Oral Appliance
- 3) Gather CPAP data from "Airview" or Data card: CPAP pressure, leakage, AHi,
- 4) Gather oxygen saturation data from Pulse Oximeter: Nadir and T90
- 5) Optional verification (PSG or HST)

- Data Storage and Confidentiality- Data will be safeguarded by assigning study participants anonymous identification numbers. Depending on relevant data, it will be stored in a password protected computer with encrypted files in the sleep lab at the Pulmonary & Sleep Center of the Valley to which sub-investigator, [name] may access. At [name], D.D.S., PA and [name] Dental Sleep Medicine, PLLC facilities data will be on a password protected computer with encrypted files to which [name] and research coordinator [name] may access.
- Transition from Research Participation - subjects are patients of record of the clinics.

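### No baseline-adjusted comparison of CNMI with the preferred mask is stated, although five outcomes are listed at the start and at month 2; the issue is precision, not bias

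*Combined protocol and SAP*

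**What the plan says.** Methods and Procedures (Data Analysis and Data Monitoring) names the methods as "using, but not limited to, the Kolmogorov-Smirnov test, Student's *t* test or the Wilcoxon rank- sum test", plus the software. The list is open. It does not tie a test to an outcome, a month or a contrast. It also leaves open whether a t test is paired, and whether it uses month-2 values or changes. No covariate or model appears anywhere in the document.

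The Background says that the study will "prospectively and randomly assign patients to one of the two combination therapy options". The same sentence goes on to say that patients use each one for two months, while Methods and Procedures describes two groups of at least 25.

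The visit lists give these start sources:

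- **Item 3:** "Obtain CPAP data from PAP titration or autoPAP: CPAP pressure, Leakage, Apnea-Hypopnea Index", followed by nadir, T90 and hours of usage.
- **Item 4:** "Home Sleep Test (HST): AHi, Nadir, T90".
- **Item 5:** a separate autoPAP entry for AHI and mask leakage.

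On the origin of the start CPAP data, Methods and Procedures says that patients "underwent a PAP titration during an overnight PSG or were assigned an autoPAP and had accumulated at least one month of data".

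Months 1 and 2 each list Airview "or Data card: CPAP pressure, leakage, AHi", then "Gather oxygen saturation data from Pulse Oximeter: Nadir and T90", and an optional PSG or HST.

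**The concern.** CNMI against preferred mask is the only randomised contrast in the study. At the minimum size, an unadjusted comparison can detect only large differences. The Purpose section speaks of data from before, during and after treatment, yet no method is given for using the values from before. Five outcomes already have a start value that could serve as a covariate, so precision may be given up at almost no cost.

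The silence also leaves several choices open until the data are seen: month-2 value, change or adjusted value; which of up to three start sources; raw or transformed scale. As the working shows, these choices can differ in power by more than ten points.

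**Working it through.** **The plan's own figure.** At least 50 patients (25 per group), with 50-100 in Criteria for Subject Selection. No alpha, power, effect size or SD is given, so the number can be neither reproduced nor called wrong.

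**Which outcomes have a start and month-2 pair**

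| Outcome | Start source (item) | Month 2 |
|---|---|---|
| CPAP pressure | 3 | Airview or data card |
| Leakage | 3, 5 | Airview or data card |
| AHI | 3, 4, 5 | Airview or data card |
| Nadir, T90 | 3, 4 | Pulse oximeter |
| Hours of usage | 3 | not listed |
| ESS | not listed | not listed |

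That makes five pairs. They match by variable, not by measurement. Start CPAP data precede combination therapy and come from one titration night or from at least a month of autoPAP, whereas month-2 data are recorded during combination therapy. The start list does not say on which treatment the HST is recorded. The oral-appliance verification test in Methods and Procedures is a possible origin, but this is not confirmed.

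**Assumptions (not in the documents).** Parallel arms, n = 25 per arm, two-sided 0.05, 80% power, no dropout, normal outcomes on the analysis scale. Rho is the within-arm correlation between the start and month-2 values.

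**Formulas (noncentral t, in SD units)**

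- Unadjusted: variance 2/n, with 2n - 2 degrees of freedom.
- ANCOVA with k covariates: variance (2/n)(1 - rho²)(1 + k/(2n - 3 - k)), with 2n - 2 - k degrees of freedom. Here k = 1 is the start value alone. k = 2 adds an indicator for titration or autoPAP source, taken as unrelated to the outcome.

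Unadjusted: √(2/25) = 0.283. The noncentrality needed for 80% power is about 2.86, so the detectable difference is 2.86 × 0.283 = 0.81 SD. The normal approximation gives 2.80 × 0.283 = 0.79.

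Example, k = 1 and rho = 0.5: 0.08 × 0.75 × (1 + 1/46) = 0.0613; √0.0613 = 0.248; 2.86 × 0.248 = 0.71 SD.

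| rho | Detectable, k = 1 | Detectable, k = 2 | Power for 0.7 SD, k = 1 | Power for 0.7 SD, k = 2 |
|---|---|---|---|---|
| 0 | 0.82 | 0.83 | 67% | 66% |
| 0.2 | 0.80 | 0.81 | 69% | 68% |
| 0.3 | 0.78 | 0.79 | 71% | 70% |
| 0.5 | 0.71 | 0.72 | 79% | 78% |
| 0.7 | 0.58 | 0.59 | 92% | 91% |

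Unadjusted power for 0.7 SD is 68%. Break-even is rho 0.15 for k = 1 and 0.21 for k = 2. At 50 per arm with k = 2, the detectable difference is 0.57, 0.55, 0.50 or 0.41 SD at rho 0, 0.3, 0.5 or 0.7, against 0.57 unadjusted.

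**Change scores (equal SDs assumed).** 0.809 × √(2(1 - rho)) = 0.96, 0.81 or 0.63 SD at rho 0.3, 0.5 or 0.7. This is worse than ANCOVA at each rho, and worse than no adjustment when rho is below 0.5.

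**Scale (simulated log-normal outcome, shift of 0.7 log-SD, 25 per arm, ANCOVA with source indicator)**

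| rho | Rank-sum | ANCOVA, log scale | ANCOVA, raw scale |
|---|---|---|---|
| 0 | about 65% | 66% | 49% |
| 0.2 | about 65% | 68% | 50% |
| 0.3 | about 65% | 70% | 51% |
| 0.5 | about 65% | 78% | 56% |
| 0.7 | about 65% | 91% | 69% |

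Raw-scale ANCOVA is therefore less powerful than the rank-sum test at rho 0.5 or less, and exceeds it only at about 0.7.

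**The case against.** The strongest reply is that this is a preference. The named tests are valid, the open list already permits ANCOVA, and the gain depends on a correlation that the documents do not give and that may be low. With the source indicator, adjustment loses 2 power points at rho 0, gains nothing at 0.2 and gains 2 points at 0.3. All of this is correct. It limits the size of the point but does not remove it: the loss is bounded at about 2 points, the gain is 10 points or more at rho 0.5 or above, and no new measurement is needed. A covariate also needs only correlation, not the same device or scale, so ANCOVA tolerates the change of instrument better than a change score does.

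Three further objections stand in part:

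- **Design.** The Background wording can be read as a crossover. If that is the design, a between-arm ANCOVA at month 2 is the wrong model.
- **Scale.** The simulation used pure log-normal data, which favour a log model. In an illustrative check of log(x+1) with many zeros and no indicator, ANCOVA was within about 2 points of the rank-sum test at rho 0.3 or less, and 7 to 8 points better at 0.5.
- **Order.** No primary outcome is named, and that choice comes first.

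A reader might infer that the plan's comparison is biased or invalid, or that the plan rules out adjustment. The documents support neither. Under proper randomisation an unadjusted test is unbiased, and the list is expressly open.

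**Conclusion.** The point holds as a low-cost improvement to consider. The plan states no baseline-adjusted comparison for its one randomised contrast, although five outcomes have a listed start value. At the minimum size, adjustment would move the detectable difference from 0.81 SD to between 0.82 and 0.58 SD over rho 0 to 0.7 (0.83 to 0.59 SD with a source indicator).

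It would be tempting to conclude that adjustment is certain to raise power. That does not follow, because rho is unknown and may lie near or below break-even. The figures rest on the assumptions listed in the working and lapse if the design is a crossover. The point does not settle the choice of primary outcome, nor the comparison with CPAP or oral appliance alone.

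**What to change.** 1. Reconcile the Background sentence on using each option for two months with the two groups in Methods and Procedures. If the design is a crossover, specify a within-patient analysis instead of the steps below.
2. If it is parallel, state that the arms are compared at month 2 by ANCOVA on arm plus the start value of the same variable, first for whichever outcome is named primary. Report the adjusted difference with its 95% CI, with the rank-sum test as a sensitivity analysis.
3. Name one start source per outcome in advance: item 3 or 4 for nadir and T90; item 3, 4 or 5 for AHI; item 3 or 5 for leakage; item 3 for CPAP pressure. Add a titration/autoPAP indicator only where the chosen source mixes the two.
4. Fix the scale in advance for skewed outcomes, for example log(x+1) for AHI, leakage and T90, and state the scale for nadir.
5. State that hours of usage and ESS are compared unadjusted unless a start and month-2 pair is added to the visit lists.

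The cost is one analysis paragraph, a choice of source and scale for each of five outcomes, and a recorded source per patient where the indicator is used. The five paired outcomes need no new measurements. If rho is near 0, 1 to 2 power points are lost.

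### The AHI source for the before-after contrast with oral appliance alone is unspecified, and using the one follow-up AHI listed for everyone would confound treatment with instrument; hours of usage and ESS also need reconciling

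*Combined protocol and SAP*

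**What the plan says.** The Purpose of the study sets two questions: whether either technique improves tolerance of CPAP, and whether either is superior to CPAP alone or OAT alone. Methods and Procedures randomises to two groups, CNMI or preferred mask, and both use PAP together with the appliance.

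The OAT-alone AHI is the entry test for partial responders: "when tested with an HST or in-lab PSG, the AHI was greater than or equal to 5 (verification sleep test". The start-of-study list also has "Home Sleep Test (HST): AHi, Nadir, T90". CPAP-alone data come from a titration PSG or from at least a month of autoPAP use.

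The month 1 and month 2 lists are identical. The AHI item is "Gather CPAP data from 'Airview' or Data card: CPAP pressure, leakage, AHi", followed in both lists by a comma and nothing more. The sleep-test item is "Optional verification (PSG or HST". The analysis paragraph names some tests but no AHI source and no primary endpoint.

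On hours of usage and the ESS, the Background says the one- and two-month data "will include: AHI, CPAP pressure, and mask leakage, Nadir, T90, hours of usage and ESS". The start list ends its CPAP item with "Time percent below 90 (T90), hours of usage". The instrument list in Methods has "CPAP Airview or Data Card: AHI, CPAP pressure, leakage", without hours.

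**The concern.** With no group on OAT alone, randomisation cannot answer the OAT question. The before value comes from a sleep test. The after value, if the visit lists are followed as written, comes from the PAP machine. In that case instrument and treatment change at the same point in every patient, and no analysis of those data can separate the two. A significant fall in AHI could then be reported as superiority over OAT when part or all of it is method.

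Hours of usage matter for two reasons. A device records events only while it is in use, so hours show how much of the night the device AHI covers. They are also the objective before-after measure of use in patients selected for CPAP intolerance. If the follow-up lists are followed as printed, there is a start value and nothing to compare it with.

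**Working it through.** **Step 1. AHI source by treatment state (Methods and Procedures).**

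| State | AHI source | Status |
|---|---|---|
| OAT alone, before | HST or in-lab PSG | part of the partial-responder definition |
| CPAP alone, before | titration PSG or autoPAP data | one or the other |
| Combination, months 1 and 2 | PAP-device download | listed without qualification |
| Combination, months 1 and 2 | PSG or HST | optional; no rule on who or which type |

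For OAT alone, the before source and the unqualified after source never match. For CPAP alone, they match only in patients whose start data came from a home device. For CNMI against preferred mask at follow-up, the source is the same in both groups.

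**Step 2. Hours of usage and ESS by place in the document.**

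| Item | Background, one and two months | Methods instrument list | Start list | Month 1 and 2 lists |
|---|---|---|---|---|
| Hours of usage | yes | no | yes | no |
| ESS | yes | no | no | no |

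**Step 3. What the before-after mean estimates.** Take device AHI on combination minus HST/PSG AHI on OAT. Its expected value is T + M + R, where T is the treatment effect, M the difference between methods and R regression to the mean. R arises because patients enter only if the OAT test gave an AHI of at least 5, and that same test supplies the before value. There is one observed mean and three unknowns. Matching the test type removes M. It does not remove R, and there is no concurrent OAT group from which to estimate R.

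**Step 4. Direction of M.** Leaving out mask-off hours would, taken alone, tend to favour the combination if whole-night AHI is the target. The scoring difference between device and sleep test is not given and could run either way. No net direction can be claimed.

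**Step 5. Illustration of size.** The plan gives no alpha, SD, effect size or offset, so there is no figure of its own to reproduce. Assume T = R = 0, an offset of d SDs of the paired differences, and a two-sided 5% paired t test. The rejection rate follows from the noncentral t distribution with n − 1 degrees of freedom and noncentrality d√n. Only n comes from the plan: 25 is the minimum per group, 50 the minimum total and 100 the maximum.

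| n | d = 0.1 | 0.2 | 0.3 | 0.5 |
|---|---|---|---|---|
| 25 | 0.077 | 0.161 | 0.302 | 0.670 |
| 50 | 0.107 | 0.284 | 0.548 | 0.934 |
| 100 | 0.168 | 0.508 | 0.844 | 0.999 |

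Hand check for n = 50, d = 0.2: d√n = 0.2 × 7.071 = 1.414. The normal approximation gives Φ(1.414 − 1.960) + Φ(−1.414 − 1.960) = 0.293, close to the exact 0.284. The rates are the same for a negative d. The bias itself is d at every n; only the chance that it reaches significance rises with n.

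**Step 6. Precision left after restricting to the same source.** The 95% half-width for a paired mean is t(0.975, n − 1)/√n in SDs of the differences. It is 0.284 at n = 50. If 25 of 50 have home-device start data (assumed), it is 0.413. For the matched-test OAT subset, assume uptake of 25% to 75% and matching test type in 50% to 100% of those tested: 50 × 0.25 × 0.50 = 6.25 and 50 × 0.75 × 1.00 = 37.5, so about 6 to 37 patients, with half-widths of 1.05 to 0.33 SD.

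**The case against.** The strongest reply is that the plan nowhere commits to setting device AHI against sleep-test AHI. PSG and HST are listed AHI sources, and both are possible at each follow-up. That stands. A reader might infer from the visit lists that a mixed comparison is planned, but the documents support only that the source is open and that a mixed comparison is what the one unqualified item would produce.

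A second reply concerns hours of usage. Both download items end in a comma, so text may have been lost, and the Background does promise hours. The instrument list in Methods is weak corroboration, because it names hours under no instrument although the start list collects them. It would therefore be too strong to say that hours will not be collected. What stands is that the printed passages disagree. ESS does not share this doubt to the same degree, since it appears in no collection list at all.

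Third, a reader might infer that tolerance would go unmeasured. It would not: the CPAP intolerance questionnaire is listed at the start and at both follow-ups, and Methods defines intolerance by patient report. Only the objective measure of use is at risk.

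Fourth, oximetry at both follow-ups gives nadir and T90 for everyone. This helps, but the start HST item does not say whether the appliance was worn, and the instrument changes there too.

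Finally, the rejection rates are generic: any offset would produce them. They show sensitivity and are not an estimate for this trial. The true treatment effect may be much larger than any offset, but the documents give neither.

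**Conclusion.** The point holds in conditional form and should be fixed. The AHI source for the OAT-alone contrast is unspecified. If the follow-up AHI listed for everyone is used, treatment is confounded with instrument, by an amount and in a direction the documents do not give. Under an assumed offset of 0.1 to 0.5 SD and no treatment effect, a nominal 5% test at n = 50 would reject between 11% and 93% of the time.

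Two wider readings are not supported. The randomised CNMI versus preferred-mask comparison is not affected by a source mismatch, although device AHI may cover different parts of the night in each group if hours differ. And measurement source is not the only obstacle to attribution: with perfectly matched tests, regression to the mean and the absence of a concurrent OAT group would remain.

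Separately, the Background and the visit lists disagree on hours of usage and ESS. Confidence is medium, because of the possible lost text after the comma and because no AHI analysis is spelled out.

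**What to change.** 1. Reconcile the Background with Methods and Procedures. Add hours of usage to the month 1 and month 2 download items and to the device line of the instrument list. Add ESS to the start, month 1 and month 2 lists. Report hours by group beside every device AHI.
2. State that AHI is compared only within the same source. Against CPAP alone, use device with device, in patients who have home-device start data. Against OAT alone, use HST with HST or PSG with PSG, where both exist.
3. Make no claim of AHI superiority over OAT from device AHI. Label the matched-test contrast exploratory, and give the reasons: uptake of the optional test follows no rule, there is no concurrent OAT group, and selection on the OAT test result brings regression to the mean.

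The cost is analysis wording, one further item from a download already taken, and the ESS at three visits. No new visit or sleep test is needed. The downside is fewer patients in the AHI contrasts, with the loss of precision shown in the working, and no full-sample AHI claim over OAT. A full-sample answer would require the optional test to become mandatory and matched in type to the OAT test. That is a new cost, is not asked for here, and would still leave regression to the mean.
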